12.4 Statistical Methods

12.4.1 Primary Analysis and Associated Planned Analyses

The primary analysis will be performed on the ITT subject population, which consists of all randomized and treated subjects. The change from baseline to Week 48 in the LogMAR acuity will be the primary response. The ETDRS score will not be directly used because there is a clear relationship between the mean and variance and according to Taylor's power law ($\log SD^2 = 1.743 \log \text{mean} + 0.48$, $R^2 = 0.839$) the best transformation is the logarithm (slope close to 2 and ease of interpretation of the difference in means of log). Because LogMAR is a logarithmic scale and is well known by ophthalmologists, this scale is retained as the primary one. The change from baseline of the treated eye will be compared to the change from baseline of the sham eye using a mixed model including the subject, the treatment and the baseline as covariates.

The center will not be included in the analysis as the number of subjects recruited per site will be very small. The difference in the mean change from baseline to Week 48 between the two treatment groups and associated 95% confidence interval will be reported. Alternative non parametric analysis (signed Wilcoxon test) will be performed as a sensitivity analysis to decrease the influence of possible outliers.

The treatment effect reflects well the effect on the better- and worse-seeing eye if no marked interaction between the eye status (better- versus worse-seeing) and treatment exists. To verify this hypothesis, a model including the subject as a random factor, the treatment as a fixed factor as well as the eye status (better- or worse-seeing) and the interaction between eye status and treatment will be fitted. If the P-value of the interaction test is below 0.15 a potential interaction is detected. In that case the better-seeing eye treated with GS010 will be compared to the better-seeing eye treated with sham and the worse-seeing eye treated with GS010 will be compared the worse-seeing eye treated with sham in an ANCOVA model including the LogMAR at baseline and the treatment. The study is then powered ($1-\beta = 0.8$) to detect a difference of approximately 30 letters between the two treatments.

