#### Primary Analysis for EMA

The null and alternative hypotheses for the primary endpoint are defined below

$$H_0: \mu_{\text{All-GS010}} = \mu_{\text{All-Sham}}$$

$$H_1: \mu_{\text{All-GS010}} \neq \mu_{\text{All-Sham}}$$

Where  $\mu$  presents the mean change from baseline to Week 48 in LogMAR. “All” represents all eyes treated with GS010 or Sham

The primary analysis will be performed on the ITT population. The change from baseline to Week 48 in the LogMAR acuity will be the primary response. The change from baseline of all-GS010 eyes will be compared to the change from baseline of all-Sham eyes (intra-subject comparison) using a mixed model of analysis of covariance (ANCOVA) using the following terms (or covariate) in the model:

- Subject as random factor
- Eyes of the subject as random factor,
- Treatment and the
- Baseline LogMAR for each eye.

The analysis will be performed based on alpha of 0.05. The statistical significance in favor of GS010 against sham will provide evidence of the advantage of using GS010 for halting visual acuity loss or improving visual acuity in subjects with LHON with duration of vision loss of more than 6 months and up to 12 months. The difference in the mean change from baseline (adjusted mean difference) to Week 48 between the two treatment groups and associated 95% confidence interval will be reported.

The center will not be included in the analysis as the number of subjects recruited per site will be very small. However, stratification by geographical area will be performed as a sensitivity analysis. Neighboring countries can be pooled together to reach at least 9 subjects per geographical entity. The pooling will be performed during the masked review of data.

An additional model will add the treatment by geographical interaction for lack of generalizability of treatment effect purposes.

All the model diagnostics will be checked.

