#### Secondary analysis of primary variable for EMA

Secondary Analysis of primary variable for EMA will be based on the methodology for primary analysis of primary variable for FDA stated below using ANCOVA. For secondary analysis change of LogMAR from baseline at Week 48 will be compared between best-seeing GS010 eyes and best-seeing Sham eyes (inter-subject comparison). Also for secondary analysis change of LogMAR from baseline in worst-seeing eyes treated with GS010 will be compared worst-seeing eyes treated with Sham.

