### Primary Analysis for FDA

The null and alternative hypotheses for the primary endpoint are defined below

$$H_0: \mu_{\text{best-GS010}} = \mu_{\text{best-Sham}}$$

$$H_1: \mu_{\text{best-GS010}} \neq \mu_{\text{best-Sham}}$$

Where  $\mu$  presents the mean change from baseline to Week 48 in LogMAR and “best” indicates best-seeing eyes.

The primary analysis will be performed on the ITT population. The change from baseline to Week 48 in the LogMAR acuity will be the primary response. The change from baseline of the best-GS010 eyes will be compared to the change from baseline of the best-Sham eyes (inter-subject comparison) using analysis of covariance (ANCOVA) including treatment as a main effect

- and baseline LogMAR

as a covariate in the model. The analysis will be performed based on alpha of 0.05. The statistical significance in favor of Best-GS010 eyes against Best-sham eyes will show evidence of the advantage of using GS010 in the best eye for halting visual acuity loss or improving visual acuity in subjects with LHON with a duration of vision loss of more than 6 months and up to 12 months. The difference in the mean change from baseline (adjusted mean difference) to Week 48 between the two treatment groups and associated 95% confidence interval will be reported.

The center will not be included in the analysis as the number of subjects recruited per site will be very small. However, stratification by geographical area will be performed as a sensitivity analysis. Neighboring regions will be pooled together to reach at least 9 subjects per geographical entity. The pooling will be performed during the masked review of data. An additional model will add the treatment by geographical area interaction to test for lack of generalizability of treatment effect.

The same analysis will be repeated for worst-GS010 eyes against worst-Sham eyes.

All the model diagnostics will be checked.

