## **9.5.5 Secondary Variables**

### GCL thickness/volume and topographical map

The change of RGC layer thickness/volume and topographical map from baseline to week 48 will be based on ANCOVA including the subject and the eyes of the subject as random factors, the treatment, and the baseline GCL thickness/volume as covariates in the model. The analysis will be performed based on alpha of 0.05. The difference in the mean change from baseline (adjusted mean difference) to Week 48 between the two treatment groups (all-GS010 vs all-Sham and best-GS010 vs best-Sham) and associated 95% confidence interval will be reported.

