### RNFL temporal quadrant and papillo macular bundle

The change of RNFL temporal quadrant and papillo macular bundle from baseline to week 48 will be analyzed same way as GCL volume and topographical map.

### Change from baseline of the LogMAR scores at Week 96

The treatment estimate at Week 96 will be based on the same statistical approach as the primary endpoint analysis for EMA between all-GS010 and all-Sham and Best-GS010 vs Best-Sham.

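### The OCT best-eye comparisons carry random subject and eye terms that one eye per subject cannot support; in the EMA primary the same eye term is an ambiguous duplicate of the residual

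*SAP*

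**What the plan says.** **EMA primary (SAP 9.5.1).** The response is one change per eye, baseline to Week 48, and the comparison is within subject. The model has random subject, treatment, each eye's baseline LogMAR and, as a separate bullet, "Eyes of the subject as random factor". Protocol 12.4.1 has no eye term: the analysis is done "using a mixed model including the subject, the treatment and the baseline as covariates".

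**FDA primary (SAP 9.5.1).** Best-seeing eyes given GS010 are compared with best-seeing eyes given sham, which the SAP calls inter-subject, "using analysis of covariance (ANCOVA) including treatment as a main effect" with baseline LogMAR as covariate and no random term. The EMA secondary analysis of best and worst eyes "will be based on the methodology for primary analysis of primary variable for FDA stated below using ANCOVA".

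**OCT (SAP 9.5.5).** The GCL model is an "ANCOVA including the subject and the eyes of the subject as random factors", with treatment and baseline GCL. The adjusted difference is to be reported "between the two treatment groups (all-GS010 vs all-Sham and best-GS010 vs best-Sham". RNFL "will be analyzed same way as GCL volume and topographical map".

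**Week 96 LogMAR (SAP 9.5.5).** The approach is that of the "primary endpoint analysis for EMA between all-GS010 and all-Sham and Best-GS010 vs Best-Sham".

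**Time course (SAP 9.5.5).** The repeated-measures model has random subject, random eyes of the subject and an unstructured covariance. It is repeated in best eyes alone and worst eyes alone, and a similar model serves visual field, contrast sensitivity and colour vision.

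The SAP does not define the eye factor and names no denominator-df method. Section 9 names only the software.

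**The concern.** A random effect can be estimated only if the data hold replication below its level. At a single visit there is one change per eye, so nothing lies below the eye except the residual. In a best-eye comparison there is one eye per subject, so nothing lies below the subject either. Listing these terms as random factors asks for variances that the data cannot separate.

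For OCT this means that the written best-eye model cannot be fitted as stated and disagrees with the model the SAP uses elsewhere for the same kind of comparison. For the EMA primary, the term departs from the protocol's model on one reading and leaves the df, and so the p-value and interval, to whatever rule is applied. Protocol Appendix V bars SAP amendment once the randomization code is broken, so the choice has to be written down before then.

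**Working it through.** **Inputs.** 36 subjects, effect 0.3 LogMAR, SD of the between-eye difference 0.594, power 84% (SAP 3.3). Two eyes per subject, one GS010 and one sham (SAP 3.4). Alpha 0.05, taken as two-sided from the not-equal alternative (SAP 9.5.1). Efficacy visits are Weeks 2, 4, 8, 12, 24 and 48 (six), plus 72 and 96 (eight); Day 1 is safety only (Protocol 6.1.4.1).

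**1. The plan's own figure.** 0.3/0.594 = 0.505 and 0.505 × √36 = 3.03. A paired t-test with 35 df has power 83.8%, which matches the stated 84%.

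**2. OCT best-eye comparison: 36 eyes, one per subject.** The covariance is (σ²_subject + σ²_eye + σ²_residual)·I, so 1 of 3 variances is identified.
- Plain ANCOVA (intercept, treatment, baseline): 36 − 3 = 33 df.
- With random subject alone, rank[X Z] = 36 and 36 − 36 = 0, before any eye term is added.

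The GCL model has no eye-status term, so the best-eye contrast cannot be taken from the all-eyes fit; it needs this subset.

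**3. EMA primary: 72 eyes.** With eye nested in subject, the covariance is σ²_subject·J (J = 1 for two eyes of the same subject) + (σ²_eye + σ²_residual)·I. The REML information matrix has rank 2 for 3 variance parameters.
- Subject only: rank[X Z] = 38, so 72 − 38 = 34.
- Subject plus nested eye: rank[X Z] = 72, so 72 − 72 = 0.
- Right/left side crossed with subject: rank[X Z] = 39, so 72 − 39 = 33. All 3 variances are then identified, but the side variance rests on two levels.

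In a simulated data set, moving 0, 25, 50 or 90% of the residual variance to the nested eye term left the REML log-likelihood, treatment estimate and standard error the same.

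**4. What this does to the primary result.** SE = 0.594/√36 = 0.099. At 34 df the critical t is 2.032, the 95% half-width 2.032 × 0.099 = 0.201 LogMAR, and power 83.7%. Satterthwaite df (generalised inverse; baselines simulated; assumed between-eye correlation 0 to 0.8) run from 34.9 down to 34.5, the same with or without the nested eye term. For an illustrative observed difference of 0.20, t = 2.02, and p = 0.0513 at 34 df or 0.0511 at 34.89 df.

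**5. Time-course model.** An unstructured matrix of size k has k(k+1)/2 parameters; the two random terms add 2.

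| Reading | To Week 48: parameters v identified | To Week 96 |
|---|---|---|
| Unstructured within eye (21; 36) | 23 v 22 | 38 v 37 |
| Unstructured across both eyes (78; 136) | 80 v 78 | 138 v 136 |
| One-eye subgroups (21; 36) | 23 v 21 | 38 v 36 |

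Within eye, the eye term is already contained in the unstructured matrix, but the subject term is not, since it supplies the covariance between eyes. Across both eyes, and in the one-eye subgroups, both terms are contained.

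**The case against.** The best defence of the EMA primary is that the list merely names the two levels, subject and eye within subject, the second being the residual. That stands as a possible reading: the model is then the protocol's and only the wording is wrong. It does not help OCT, where the subject term alone already uses up every observation, and the right/left reading fails there for the same reason.

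It can also be said that the OCT section is loosely drafted: the model is in one sentence, the comparisons in a later one, and ANCOVA without random terms was intended for best eyes. That may be the intent, but the section gives no other model.

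A singular fit might well surface before unmasking, through the model diagnostics (SAP 9.5.1), the table runs and masked review (SAP 8.2) or program validation (Protocol Appendix V). That is fair, but none of these steps names a df rule.

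Three stronger inferences are not supported:
- A reader might infer that the EMA primary conclusion is at risk. The estimate and standard error do not move. Zero df gives no usable test and would force a correction. The alternative 72 − 3 = 69 df ignores the subject term in a comparison that the SAP calls intra-subject.
- A reader might infer that Week 96 LogMAR in best eyes has the OCT error. The cross-reference can mean the EMA primary model or the ANCOVA that the EMA secondary analysis prescribes for best eyes; the text allows both.
- A reader might infer that eye status, on which allocation is balanced, is wrongly missing from the EMA primary. It is a prespecified sensitivity covariate (SAP 4.3 and EMA sensitivity analysis 8). It is also defined first by baseline acuity, and baseline LogMAR is already in the model.

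**Conclusion.** The OCT best-eye models for GCL and RNFL are wrong as written: 1 of 3 variances identified and 0 residual df by N − rank[X Z], against 33 for plain ANCOVA, in conflict with the SAP's own FDA model. These analyses are supportive (SAP 9.5.3).

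In the EMA primary there is a minor specification defect. It depends on reading the term as eye within subject, and it leaves the p-value and interval undetermined only because no df method is named; Satterthwaite-type methods give about 34 to 35 df either way.

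The time-course model is over-parameterised on either reading of the unstructured covariance, by one or two parameters.

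The counts assume 36 subjects with complete data. The rank results do not depend on the simulated baselines; the Satterthwaite df do, slightly.

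**What to change.** Before unmasking:

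1. Delete the random eye term from the EMA primary and from the all-eyes models that copy it: the FDA secondary analysis, GCL, RNFL and Week 96 LogMAR. Keep subject random and name the df method, for example Kenward-Roger.
2. For every single-visit best-eye or worst-eye comparison, including GCL and RNFL, use the FDA primary's ANCOVA: treatment plus the variable's own baseline, no random terms. Say explicitly that this applies to Week 96 LogMAR.
3. In the time-course model and those modelled on it, state the span of the unstructured covariance. Either use unstructured within eye plus random subject (22 parameters to Week 48, 37 to Week 96, all identified), or unstructured across both eyes with no random terms (78 and 136, a heavy demand on 36 subjects). Use no random terms in the one-eye subgroups.

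The cost is SAP wording only. Sample size and data collection do not change, and primary power stays at 83.7% with 34 df.

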#### Secondary analysis of primary variable for EMA

Secondary Analysis of primary variable for EMA will be based on the methodology for primary analysis of primary variable for FDA stated below using ANCOVA. For secondary analysis change of LogMAR from baseline at Week 48 will be compared between best-seeing GS010 eyes and best-seeing Sham eyes (inter-subject comparison). Also for secondary analysis change of LogMAR from baseline in worst-seeing eyes treated with GS010 will be compared worst-seeing eyes treated with Sham.

### Other Analysis

Summary statistics for LogMAR and ETDRS score and change from baseline will be presented by treatment group (All-GS010/All-Sham).

A graph presenting the mean of each treatment group at baseline and the mean at Week 48 will be presented. The graph will be useful to assess whether the difference in the change from baseline is mainly due to the difference at baseline or the difference at Week 48.

### Sensitivity Analyses

The primary analysis with the same model will be repeated for the following lists.

- 1) Per protocol
- 2) Randomized subjects even if they were not treated and assigned treatment by randomization instead of actual treatment received
- 3) Secondary handling of missing data
- 4) Model with geographical area effect
- 5) Model excluding major outliers if any
- 6) Analysis of absolute Week 48 LogMAR values
- 7) Baseline GCL thickness/volume and topographical map
- 8) Best or worst-seeing eye (eye status) added as a binary covariate
- 9) Duration of vision loss at the time of treatment added as a covariate in the model

All these analyses will be presented in a forest plot displaying treatment effect, 95% confidence intervals and p-value. The analysis will also be presented in tabular format.

- 10) Non-parametric Analysis: Wilcoxon signed-rank test will be performed as a sensitivity analysis to compare between all-GS010 eyes and all-Sham eyes

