### 5.3 CHANGE FROM BASELINE

The change from baseline value is defined as the value at a given time point minus the baseline value.

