#### Sensitivity Analysis

Primary analysis with the same model will be repeated for the following lists.

- 1) Per protocol
- 2) Randomized subjects including those not treated
- 3) Secondary handing of missing data
- 4) Model with country effect
- 5) Model excluding major outliers if any (defined as a standardized endpoint greater than the absolute value of 4.0)
- 6) Analysis of absolute Week 48 LogMAR values, without covariate adjustment
- 7) Baseline GCL layer thickness/volume and topographical map
- 8) Duration of vision loss at the time of treatment as a covariate

All these analyses will be presented in a forest plot displaying treatment effect, 95% confidence intervals and p-value.

10) Non-parametric Analysis: Wilcoxon Rank-Sum test will be performed as a sensitivity analysis to compare between Best-GS010 eyes and Best-Sham eyes.

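### EMA sensitivity analysis 6, fitted with the same model as written, reproduces the EMA primary analysis exactly and so tests nothing

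*SAP*

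**What the plan says.** Under Primary Analysis for EMA, SAP 9.5.1 states: "The change from baseline to Week 48 in the LogMAR acuity will be the primary response". The listed model terms include "Subject as random factor", a random term for eye, treatment, and "Baseline LogMAR for each eye". SAP 5.3 fixes the arithmetic of the response: "The change from baseline value is defined as the value at a given time point minus the baseline value".

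The EMA list under Sensitivity Analyses opens with "The primary analysis with the same model will be repeated for the following lists". Item 6 is "Analysis of absolute Week 48 LogMAR values" and says nothing about removing baseline. The first nine items go into a forest plot with effect, 95% confidence interval and p-value, and into a table.

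The corresponding item 6 in the FDA list is worded differently: "Analysis of absolute Week 48 LogMAR values, without covariate adjustment".

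**The concern.** A sensitivity analysis is informative only if it could give a different answer from the primary. Under the EMA wording, item 6 changes the response but keeps the baseline covariate, and those two choices cancel. Its row must fall exactly on the primary estimate whatever the data are. A reader of the forest plot could take that agreement as evidence that the result does not depend on analysing change rather than the final value, when no such evidence has been produced.

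The SAP does care about this question. Under Other Analysis for EMA it plans a graph of group means at baseline and Week 48, to show which of the two time points drives a difference in change. A modelled comparison of Week 48 values without baseline adjustment would address the same question with an estimate and an interval. The EMA wording does not deliver one.

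**Working it through.** **Scale.** SAP 3.3 gives an SD of the between-eye difference in change of 0.594, a difference of 0.3 LogMAR, 36 subjects and 84% power. The paired t-test has noncentrality 0.3/0.594 × √36 = 0.505 × 6 = 3.03 on 35 df. At two-sided 0.05 this gives 83.8%, so the stated 84% reproduces. The implied standard error of the paired difference is 0.594/√36 = 0.099 LogMAR. These figures set the scale only; none of them is in dispute.

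**Algebra.** Write W for the Week 48 value, B for the eye's baseline, T for treatment, u for the subject effect and e for the remaining eye-level error.

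- Primary model: W − B = a + t·T + b·B + u + e.
- Add B to both sides: W = a + t·T + (b + 1)·B + u + e.

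The second line is item 6 fitted with the primary model. Its design matrix and random terms are the same. B is a column of the design matrix, so adding it to the response raises its own coefficient by 1 and leaves every residual unchanged. The variance components are estimated from those residuals, so they do not change either. Hence t, its standard error, its interval and its p-value are identical. This needs no assumption about variance, correlation or effect size. It also holds with imputed Week 48 values, provided the same eyes and the same imputed values enter both fits.

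**Numerical check.** REML fits of the SAP model were run on simulated trials of 36 complete pairs, with 400 trials in each of 7 scenarios, 2,800 in all. A separate random eye term was not fitted: with one Week 48 value per eye it cannot be told apart from the residual.

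Assumptions not taken from the documents: baseline SD 0.5; inter-eye baseline correlation 0 to 0.9; residual within-subject correlation 0.05 to 0.7; slope of Week 48 on baseline 0.7; four areas of 9 subjects; SD of area effects 0.2 to 0.5 LogMAR. The true effect was 0.3, and the residual was scaled to the SAP's 0.594. Mean primary standard errors were 0.094 to 0.099 across scenarios, in line with the design value above.

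| Analysis compared with the primary | Mean absolute shift in estimate (range over scenarios) | Largest shift | Trials where the p<0.05 verdict changes |
|---|---|---|---|
| Item 6, same model | zero to numerical precision | 3e-9 | none possible (identity) |
| Item 6, baseline dropped | 0.021 to 0.065 | 0.29 | 5% to 25% |

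For item 6 with the same model, the standard errors also agreed to within 2.3e-9 and the two baseline slopes differed by 1.000000.

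Relative to the primary standard error, the mean shift with baseline dropped runs from 0.0214/0.0973 = 0.22 to 0.0647/0.0938 = 0.69. The unadjusted version is therefore a different analysis that can disagree with the primary.

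**The two lists side by side.** The FDA primary is also an ANCOVA of change with baseline as covariate, so the same identity would apply there. The qualifier in FDA item 6 is what prevents it, and the EMA item lacks that qualifier.

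**The case against.** The strongest reply is that the lead-in cannot be literal, because other items in the list add terms to the model. The FDA wording also suggests that an unadjusted analysis was meant for EMA as well, so this may be a missing phrase rather than a wrong choice of analysis. That may well be the intention. But where the EMA list alters the model it does so by naming an extra term, and item 6 names no removal. A programmer following the text would keep baseline. Either way the same words need to be added.

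A second reply is that the baseline question is not left untouched. The graph of means is planned, the primary model adjusts for each eye's baseline, and item 10 adds a Wilcoxon signed-rank test. This stands. What is missing is a modelled unadjusted Week 48 estimate, not every look at baseline.

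A third reply is that SAP 9.5.3 treats every analysis other than the primary as supportive, and a duplicate row would be visible in the table. This also stands and limits the consequence.

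A reader might also infer that item 4, "Model with geographical area effect", must agree with the primary because area is constant within a subject. The documents do not support that. Without the baseline covariate, an area main effect does cancel exactly from complete pairs. The SAP model, however, carries eye-level baseline and estimated variance components, so the cancellation is not exact. In the simulations item 4 moved the estimate by 0.003 to 0.010 LogMAR on average (95th percentile 0.011 to 0.040, largest 0.105). The ratio of its standard error to the primary's ran from 0.81 to 1.14, and the verdict changed in 0.3% to 2.2% of trials. It usually moves little, but it is not a copy. The treatment-by-area model already planned in SAP 9.5.1 deals with generalizability.

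**Conclusion.** The point holds for item 6 alone. As written, that item is the EMA primary analysis under another name, and its forest-plot row carries no information. The identity rests on one reading, that the same model keeps the baseline covariate, and on no numerical assumption. The size of the difference once baseline is dropped (0.02 to 0.065 LogMAR on average, 5% to 25% verdict changes) does rest on the simulation assumptions listed above and should be taken as indicative.

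A reader should not conclude that the primary result is in doubt. The primary test, its estimate and its alpha are untouched; only the robustness displayed around it is overstated by one row. The correction is worth making, but the primary analysis does not depend on it.

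**What to change.** Word EMA item 6 as the FDA list already does: "Analysis of absolute Week 48 LogMAR values, without covariate adjustment". State the resulting model: Week 48 LogMAR as response, subject random, treatment fixed, no baseline term. Leave item 4 as pre-specified.

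The cost is a few words in the SAP and a small programming change, with no new data. The drawback is that the unadjusted row may be less precise and may differ from the primary; that possibility is what makes it a check. The change should be made before the randomization code is broken, because Protocol Appendix V allows no SAP amendment after that point and would class any addition as post hoc.
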